- Additional exploratory efficacy analyses were added to both Section 5.4.1 (Efficacy Endpoints) and Table 5.6 (Secondary and Exploratory Efficacy Variables and Analysis Methods).
- For MIDAS, the clarification is added to state that "No imputation is needed when calculating the total score, as patients are not allowed to send partial data."
- The calculation of duration of exposure to study drug was updated to use study phase disposition date (instead of derivation using half-life of LY2951742) when applicable.
- Analysis method for PGI-I was updated for clarification.
- Analyses of C-SSRS for SP IV were added.
- For categorical safety measures, analysis method was updated to Fisher's exact method instead of CMH method adjusting for pooled region1 because it is it expected that pooled region1 variable should not have any impact on safety measures.
- "Upper respiratory tract infections" replaces "infections" in Section 5.5.12.1.1.3.
- Updated the subsetting criteria for analysis of elevation in ALT, AST, ALP, and TBIL.
- Response to previous migraine prevention therapy was updated based on eCRF, and a definition of previous migraine prevention therapy was added.
- Definition of concomitant therapy was added.
- Section 5.5.1.3. Definition of geographic regions was updated.
- Section 5.5.10.2. Sensitivity analysis to assess the robustness of primary analysis for missing data assumptions was updated to use the most recent approach recommended by Permutt (2015). Due to this change, the section 7 (appendix) for selection model was removed.
- Section 5.5.10.4. Corrected a typo in the multiple testing algorithm.
- Section 5.5.12.1.6. Immunogenicity was updated to clarify the study phases that will be included for each of the immunogenicity analyses and to provide additional listings.

- Section 5.5.13. Subgroup Analysis was updated.
 - Baseline ADA status was removed, i.e., no subgroup analyses will be conducted by baseline ADA status.
 - Subgroup analyses for safety measures were removed.
- Section 5.5.14 Exploratory Analysis was deleted.
- Section 5.6. Interim Analysis was updated due to faster enrollment and enrollment rate difference between CGAG and CGAH.

Statistical Analysis Plan Version 3 was approved prior to second interim analysis (the interim analysis for primary efficacy endpoint, which is the first unblinding to study team). The SAP version supersedes the statistical plans described in the protocol.

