5.4.2. Other Efficacy Measures

5.4.2.1. Patient Global Impression

The Patient Global Impression of Severity (PGI-S) will be collected at baseline and monthly post-baseline visits. In this single-item scale, patients rate the severity of their migraine condition on a scale ranging from "not at all ill" (coded as 1) to "extremely ill" (coded as 7).

The Patient Global Impression of Improvement (PGI-I) will be collected at monthly post-baseline visits during the treatment phase.

Change from baseline in PGI-S scores will be analyzed. Patient Global Impression of Improvement scores at post-baseline visits will be analyzed by adjusting for PGI-S score at baseline.

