5.5.1. General Considerations

Treatment effects will be evaluated based on an overall one-sided significance level of 0.025 for all efficacy and safety analyses. Ninety-five percent confidence intervals (CIs) for the difference in least-square means (LSMeans) between treatment groups will be provided.

Change from baseline of continuous variables with repeated measures will be analyzed using a mixed model repeated measures (MMRM) analysis. An MMRM analysis refers to a restricted maximum likelihood (REML)-based, mixed-effects repeated measures analysis using all the longitudinal observations at each post-baseline visit. Additionally, an analysis of variance (ANOVA) or an analysis of covariance (ANCOVA) model will also be used to analyze the change from baseline to the average monthly measures during 6-month treatment phase (for measures with corresponding objectives evaluated over the 6-month treatment period), or to last observation carried forward (LOCF) endpoint (for measures with corresponding objectives evaluated at Month 6).

For other continuous variables, the change from baseline to LOCF endpoint will be analyzed using an ANOVA or ANCOVA model.

Unless otherwise specified, when an ANOVA model or ANCOVA model is used to analyze a continuous efficacy variable, type III sum-of-squares for the LSMeans will be used for the statistical comparisons.

Binary variables with repeated measures will be analyzed in a generalized linear mixed models (GLIMMIX) as pseudo-likelihood-based mixed effects repeated measures analysis.

For categorical efficacy variables without repeated measures, comparisons between treatment groups will be performed using logistic regressions to adjust for more covariates (see Section 5.5.1.1 for details). For other categorical variables without repeated measures, comparisons between treatment groups will be performed using Fisher's exact tests. Unless specified otherwise, Fisher's exact test will be used for comparisons of baseline measures (eg, baseline patient characteristics, previous therapy, etc.) and categorical safety measures; logistic regression will be used for comparisons of post-baseline efficacy measures.

For details of analysis methods, please refer to the following sub-sections.

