5.5.1.1. Adjustments for Covariates

The MMRM models will include the fixed, categorical effects of treatment, pooled region1, month, and treatment-by-month interaction, as well as the continuous, fixed covariates of baseline value and baseline-by-month interaction. The baseline value and baseline-by-month interaction are included to account for the differential influence over time that the baseline value has on the post-baseline values. Pooled region1 is defined in Section 5.5.1.3. Pooled region1 will be excluded from MMRM models for safety measures.

When an ANOVA model is used to analyze a continuous efficacy variable at the LOCF endpoint, the model will contain the main effects of treatment and pooled region1. When an ANCOVA model is used to analyze a continuous efficacy at the LOCF endpoint, the model will contain the main effects of treatment and pooled region1 and appropriate baseline value as a covariate. When an ANOVA or ANCOVA model is used to analyze a continuous safety variable, the pooled region1 will be removed from the model.

The GLIMMIX models for the repeated binary outcomes will include the fixed, categorical effects of treatment, month, and treatment-by-month interaction, as well as the continuous, fixed covariate of baseline value. Pooled region1 and the baseline value-by-month interaction will be excluded from the model in order to increase the likelihood of convergence.

When a logistic regression is used to analyze a binary variable, the model will include the main effect of treatment, pooled region1 (if appropriate), and appropriate baseline value as a covariate. Pooled region1 may be excluded from the model in case of non-convergence.

With the exception of efficacy analyses on migraine headache days or categorical analysis of response rate (such as 50% response rate) derived from migraine headache days where the continuous value of baseline migraine headache days will be used as covariate, all other efficacy analyses will include baseline number of migraine headache days category (<8 vs ≥8) as a covariate in the MMRM, AN(C)OVA, GLIMMIX and logistic regression model. Specifically, for time to event analysis of 50% response (such as Time to first 50% response in double-blind treatment phase and Time to first loss of 50% response in post-treatment phase), stratified log rank test will be used with the baseline number of migraine headache days category (<8 vs ≥8) as 1 of the covariates

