5.5.1.3. Definition of Geographic Regions

In CGAG, eligible patients will be randomized within each of the following 4 regions: United States (US) east, US west, Puerto Rico, and Canada. In CGAH (which includes additional countries from European Union (EU) and other regions), eligible patients will be randomized within each country.

In CGAH and integrated efficacy analysis, subgroup analyses for primary measure will be done by a subgroup variable of region defined below:

- North America, including the US;
- Europe, including United Kingdom (UK), Netherlands, Spain, Czech, and Germany;
- Other, including Argentina, Israel, Korea, Taiwan, and Mexico

In order to clarify the different definitions of regions and be consistent for CGAG and CGAH, 2 variables of regions are defined. Region1 is the smallest geographic area within which the randomization is done. Region2 is a larger geographic area which defines the subgroup variable of region. The definitions are summarized in Table 5.4 below.

All regions in region1 (as defined in Table 5.4 below) with fewer than 2 randomized patients per LY-treated group or fewer than 4 randomized patients in placebo group with nonmissing baseline and at least 1 post-baseline values of the number of migraine headache days will be pooled.

All analyses will use pooled region1, unless otherwise specified.

Variable Name	Definition in CGAG	Definition in CGAH
Region1 (Randomization Region)	US eastUS westCanadaPuerto Rico	• Country
Region2 (Subgroup Region)	NA* (all from one region, ie, North America, including the US and Canada)	 North America, including the US; Europe, including UK, Netherlands, Spain, Czech, and Germany; Other, including Argentina, Israel, Korea, Taiwan, and Mexico

Table 5.4. Definition of Region1 and Region2

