The number of weekly migraine headache days in Month 1 can be considered as ordinal data with possible values of 0, 1, 2, 3, 4, etc. It will be analyzed using an ordinal repeated measures model implemented using the GLIMMIX procedure in SAS. In this model, a proportional odds model with cumulative logit link will be used, and a random intercept will be applied to the observations for each patient to account for repeated measures. The model will include the fixed, categorical effects of treatment, pooled region1, week, and treatment-by-week interaction, as well as the continuous, fixed covariate of baseline number of migraine headache days and baseline number of migraine headache days by week interaction. Log (number of compliant calendar days within each week/7) will be used as the offset in the model.

Time to Event Measures

For the following time to event measures, a Kaplan-Meier curve of the time to event and treatment group comparison using log-rank test stratified by pooled region1 and baseline MHD frequency category (<8 vs ≥8 migraine headache days per 30-day period) will be provided.

- Time to first 50% response in double-blind treatment phase
- Time to first loss of 50% response in post-treatment phase
- Time to initiation of preventative treatment for migraine or probable migraine in post-treatment phase

Distribution of Response Rates

Overall x% response rate during the double-blind treatment phase will be estimated for X=0, 5, 10, ..., 95, and 100, using GLIMMIX model as described earlier in this section. These estimated response rates will be plotted and points within each treatment arm will be connected to show a curve of response rates. No statistical comparisons will be conducted among different treatment arms.

Analysis for PGI-I

The PGI-I raw value will be analyzed with a mixed model repeated measures analysis where the covariates are the fixed categorical effects of treatment, visit, and treatment-by-visit interaction, as well as the continuous fixed covariates of baseline PGI-S score and baseline PGI-S score-by-visit interaction.

Table 5.6. Secondary and Exploratory Efficacy Variables and Analysis Methods

Efficacy Variables	Analysis in SP III	Analysis in SP III/IV
Number of migraine headache hours		
Number of migraine attacks		
Number of migraine headache days with abortive (acute)		
medication use		
Proportion of migraine headache days with abortive (acute)		
medication use	MMRM,	
Number of headache days	ANCOVA ^a	

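### The PGI-I model in SAP 5.5.10.3 leaves out the baseline migraine-frequency category (<8 vs ≥8 days) that SAP 5.5.1.1 requires, so the SAP supports two different models

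*SAP*

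**What the plan says.** SAP 5.5.1.1 (Adjustments for Covariates) sets the general rules. On model structure: "The MMRM models will include the fixed, categorical effects of treatment, pooled region1, month, and treatment-by-month interaction", together with the baseline value and its interaction with month. On baseline migraine frequency, it first sets aside analyses of migraine headache days and of response rates derived from them, which use the continuous baseline count. It then states that "all other efficacy analyses will include baseline number of migraine headache days category" (<8 vs ≥8), naming the MMRM, AN(C)OVA, GLIMMIX and logistic regression models. That sentence has no clause allowing a later section to opt out.

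SAP 5.5.10.3 has a separate paragraph for the PGI-I. The raw rating is analysed by a mixed model for repeated measures "where the covariates are the fixed categorical effects of treatment, visit, and treatment-by-visit interaction", with baseline PGI-S and baseline PGI-S-by-visit as continuous terms. Nothing else is listed.

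The PGI-I is defined in SAP 5.4.2 (Other Efficacy Measures) and appears among the efficacy variables in Table 5.6. SAP 5.4.2.1 explains its special covariate: "Patient Global Impression of Improvement scores at post-baseline visits will be analyzed by adjusting for PGI-S score at baseline".

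On region, SAP 5.5.1.3 says: "All analyses will use pooled region1, unless otherwise specified".

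**The concern.** The PGI-I is in neither exception to the frequency-category rule, but the paragraph that specifies its model reads as a complete list without the category. A programmer working from 5.5.1.1 would include the term; one working from 5.5.10.3 would not. The choice should not depend on which section is read, and it would no longer be prespecified if it were made after unblinding.

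The omitted term is also a randomisation stratum (Protocol 6.2, SAP 5.3). SAP 5.5.13 groups the baseline frequency category with the subgroup variables expected to be prognostic. Omitting a prognostic stratum leaves its variance in the residual, although stratification has already removed most of its contribution to chance differences between arms. The model-based standard error is then somewhat too large.

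**Working it through.** **Term check.** The terms required by 5.5.1.1 for an efficacy MMRM outside the exceptions, against those listed for the PGI-I in 5.5.10.3:

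| Term | 5.5.1.1 | PGI-I, 5.5.10.3 |
|---|---|---|
| Treatment, time, treatment-by-time | yes | yes |
| Baseline and baseline-by-time | yes | yes, with PGI-S in place of the absent PGI-I baseline |
| <8/≥8 category | yes, no opt-out clause | not listed |
| Pooled region1 | yes, but 5.5.1.3 allows exceptions | not listed |

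The absence of a PGI-I baseline explains the PGI-S terms. It does not explain the missing category. The Version 2 entries in SAP Section 3 record both the category rule and the note "Analysis method for PGI-I was updated for clarification", and do not name the PGI-I as exempt. Other models in 5.5.10.3 do name their stratification terms: the weekly migraine-day model lists pooled region1, and the stratified log-rank tests list both pooled region1 and the frequency category. Against these, a PGI-I list with neither reads as complete.

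**Size.** The documents give no variance or stratum effect for the PGI-I, so the input is assumed. Let R² be the share of variance in the six-month mean PGI-I, beyond baseline PGI-S, that the category explains. With the arms balanced on the category by stratified randomisation:

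- ratio of the reported standard error (category omitted) to the correct one = 1/√(1 − R²)
- actual one-sided size at nominal 0.025 = 1 − Φ(1.96 × ratio)

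| Assumed R² | SE ratio | One-sided size |
|---|---|---|
| 1% | 1/√0.99 = 1.005 | 0.0244 |
| 2% | 1/√0.98 = 1.010 | 0.0239 |
| 5% | 1/√0.95 = 1.026 | 0.0222 |

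**What these R² values mean.** Take the low-frequency share at the enrolment cap in SAP 5.3: p = 578/825 = 0.7006, so p(1 − p) = 0.2098. Let d be the difference in PGI-I between the two frequency strata, given baseline PGI-S, in within-stratum SDs. Then R² = p(1 − p)d² / (1 + p(1 − p)d²), so d = √{[R²/(1 − R²)] / [p(1 − p)]}.

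- R² = 1%: d = √(0.0101/0.2098) = 0.22 SD
- R² = 5%: d = √(0.0526/0.2098) = 0.50 SD

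The assumed range thus corresponds to a difference between strata of roughly 0.2 to 0.5 SD. A raw difference that ignores baseline PGI-S would overstate the effect if frequency and PGI-S are correlated.

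**The case against.** The strongest reply is that 5.5.1.1 adds to every local model list. The text for the PGI-S, and for the MSQ and MIDAS repeated-measures models, does not name the category either; those models get it only from 5.5.1.1. Read the same way, the PGI-I model also includes it and the sections agree. This is a fair reading and probably the intended one. It reduces the defect to ambiguity, but does not remove it: those other models refer back to a general specification, whereas the PGI-I has its own list, worded as complete. The opposite reply, that the specific paragraph overrides the general rule, gives the opposite model. That both are arguable is the problem.

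Three stronger readings are tempting, and the documents do not support them.

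- A reader might infer that omitting pooled region1 is an equal breach, since 5.5.1.1 states "Pooled region1 will be excluded from MMRM models for safety measures" and the PGI-I is not a safety measure. But the opt-out wording in 5.5.1.3 lets 5.5.10.3 specify a model without region, and nothing requires a reason for each exception. SAP 5.5.13 also does not expect the broader region2 grouping to be prognostic.
- A reader might infer that SAP 5.5.1 directs programmers to the PGI-I paragraph, because it says "For details of analysis methods, please refer to the following sub-sections". The first of those sub-sections is 5.5.1.1 itself, so that sentence does not favour one model over the other.
- A reader might infer an inflated false-positive rate. The direction is the reverse: omitting a prognostic randomisation stratum makes the test slightly conservative.

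**Conclusion.** The inconsistency is real but minor. SAP 5.5.1.1 requires the <8/≥8 category in the PGI-I model, and 5.5.10.3 gives a list without it. If that list is followed, the standard error is about 0.5% to 2.6% too large for an assumed R² of 1% to 5%. Those figures rest on the assumed R² and on balance from stratified randomisation; the documents supply no PGI-I variance with which to narrow them. The PGI-I is an other secondary endpoint without multiplicity adjustment (SAP 4.2.2), so only its nominal interval and p-value are affected. The primary and key secondary analyses are not.

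**What to change.** Before unblinding at interim analysis #2, add the <8/≥8 baseline migraine headache day category to the PGI-I MMRM in SAP 5.5.10.3, so that it matches 5.5.1.1. Keep baseline PGI-S and its visit interaction as they stand. The cost is one sentence and 1 degree of freedom. Protocol 9.2 allows SAP changes only before unblinding, so the timing matters more than the effort.

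Naming the PGI-I as an exception in 5.5.1.1, with a reason, would also remove the ambiguity. Adding the category is preferable because the trial already randomises by it and the plan expects it to be prognostic.

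Pooled region1 may be added in the same sentence, to align with the stratified randomisation and the general MMRM. With 11 planned countries (Protocol 9.1) this takes at most 10 more degrees of freedom. Counting all 825 patients, the two-sided 5% t value is 1.963 both at 821 degrees of freedom and at 810, so even both additions cost almost nothing. This second step is optional.

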5.5.11. Quality-of-Life (QoL) Analyses

The mean change from baseline to each post-baseline visit for Study Period III and Study Period III/IV for MIDAS (item scores and total score), I as defined in Section 5.4.3 will be evaluated using MMRM as described in Section 5.5.10.1.

The mean change from baseline to each post-baseline visit for Study Period III and Study Period III/IV for MSQ total score and domain scores averaged across Months 4-6 will be evaluated using MMRM as described in Section 5.5.10.1. The endpoint for comparing LY2951742 with placebo will be estimated using a LSMESTIMATE statement in PROC MIXED as the average across Months 4-6.

Mean change from baseline to LOCF endpoint in the 6-month treatment phase for above quality of life measures will be evaluated using the ANCOVA model as described in Section 5.5.10.1.

The MSQ Role Function Restrictive domain responders and MIDAS responders will be analyzed using GLIMMIX. The threshold for MSQ Role-Function Restrictive Domain Response will be derived as outlined in "Statistical Analysis Plan for Psychometric Properties of the MSQ v2.1 Role Function-Restrictive Domain." The threshold for MIDAS response will be a 50% improvement from baseline in MIDAS total score.

5.5.12. Safety Analyses

The safety analyses will be conducted for Study Period III, Study Period IV, as well as Study Periods III and IV combined.

For Study Period III and Study Period IV separately, the safety analyses outlined in the following sub-sections will be conducted.

For Study Period III and IV combined, only the change from baseline with MMRM analysis (Section 5.5.10.1) will be conducted.

The safety and tolerability of treatment will be assessed by summarizing the following:

- TEAEs
 - o By PT by decreasing frequency
 - o By SOC

- o By maximum severity
- o By High Level term
- o By considered to be related to investigational produce by investigator
- SAEs
- AEs leading to discontinuation
- Suicide-Related Thoughts and Behaviors
- Vital signs and weight
- Laboratory measurements
- ECGs
- Antibodies (ADA and NAb)

The baseline and post-baseline for all safety measures are described in Table 5.5 unless specified otherwise.

As summarized in CGAG protocol addendum 2 (CGAH Protocol Addendum 7), to characterize the time course of treatment-emergent ADA, additional data will be collected after patients completed or discontinued from study. Individual patient listings of those data including concomitant medication, adverse events and ADA measurements will be created.

5.5.12.1. Categorical Safety Variables

Unless specified otherwise, the categorical safety analyses will include both scheduled and unscheduled visits. Categorical safety analyses will only be conducted for Study Period III and Study Period IV separately.

Comparisons between treatment groups for all categorical safety measures will be made using Fisher's exact test for Study Period III with the ITT population.

Descriptive statistics only will be presented for the treatment groups in Study Period IV with post-treatment population.

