Treatment emergent changes in temperature and weight	Safety population with a baseline and at least one post-baseline observation	Low: Minimum value from Visits 1-3 High: Maximum value from Visits 1-3	Low: Minimum value from Visits 3.01-12 High: Maximum value from Visits 3.01-12

Patient Population with Baseline and Post-Baseline Definitions by Study Period and Type of Analysis

			Post-baseline		
Study Period/Analysis	Patient Population	Baseline Observation	Observation(s)		
Study Period III					
Treatment emergent changes in blood pressure, pulse, and ECGs	Safety population with a baseline and at least one post-baseline observation	Low: Last non-missing from Visits 1-3 High: Last non-missing from Visits 1-3	Low: Minimum value from Visits 3.01-12 High: Maximum value from Visits 3.01-12		
Continuous safety analyses (repeated measures)	Safety population with a baseline and at least one post- baseline observation	Last of Visits 1-3	All scheduled visits 3 <visits<=12< td=""></visits<=12<>		
Continuous safety analyses—change from baseline to LOCF endpoint (ANCOVA)	Safety population with a baseline and at least one post-baseline observation	Last of Visits 1-3	Last of Visits 3.01-12		
Study Period III and IV combined					
Primary/secondary/exploratory efficacy analyses	ITT population with a baseline and at least one post-baseline observation	Visit 3	All scheduled visits 3 <visits≤14< td=""></visits≤14<>		
Quality of Life analyses	ITT population with a baseline and at least one post-baseline observation	Visit 3	All scheduled visits 3 <visits≤14< td=""></visits≤14<>		
Continuous safety analyses (repeated measures)	Safety population with a baseline and at least one post-baseline observation	Visit 3	All scheduled visits 3 <visits≤14< td=""></visits≤14<>		
Treatment-emergent immunogenicity	Safety population	Visit 3	All Visits 3.01-14		
Study Period IV					
Post-treatment–emergent adverse events	Post-treatment population	All Visits 1-12	All Visits 12.01-14		
Serious adverse events, discontinuations due to adverse events	Post-treatment population	NA	All Visits 12.01-14		
Post-treatment–emergent abnormal laboratory values	Post-treatment population with normal laboratory values at all nonmissing baseline visits (with respect to direction being analyzed) and who have at least one post-baseline observation	Low: Minimum value from Visits 1-12 High: Maximum value from Visits 1-12	Low: Minimum value from Visits 12.01-14 High: Maximum value from Visits 12.01-14		

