- Similarly, for other study phases, the baseline is defined as the last non-missing value before patients enter the study phases of interest. The baseline definition was chosen to be consistent with the analysis approach for the double blind treatment phase as described above.

This baseline definition for SBP, DBP, and pulse applies to all analyses (both continuous and categorical) for SBP, DBP, and pulse.

The baseline and postbaseline values for temperature and weight are defined below (also in Table 5.5):

- For continuous analyses of temperature and weight, last nonmissing baseline during the baseline period will be used as the baseline.
- For the analyses of categorical changes of interest in temperature and weight,
 - o the baseline is defined as the minimum value during baseline period when the direction of change is low.
 - o the baseline is defined as the maximum value during baseline period when the direction of change is high.

Table 5.7. Criteria for Categorical Changes of interest in Vital Signs and Weight

Parameter	Direction	Criteria	Patients Population defined by Baseline Categories
Systolic BP (mm Hg)	Low	≤90 and decrease ≥20	All patients; >90; ≤90
(sitting)	High	≥140 and increase ≥20	All patients; <140, ≥140
	PCS High	≥180 and increase ≥20	All Patients;<180; ≥180
	Sustained Elevation	≥140 and increase ≥20 at 2 consecutive visits	All patients; <140; ≥140
Diastolic BP (mm Hg)	Low	≤50 and decrease ≥10	All patients; >50; ≤50
(sitting)	High	≥90 and increase ≥10	All patients; <90, ≥90
	PCS High	≥105 and increase ≥15	All Patients; <105; ≥105
	Sustained Elevation	≥90 and increase ≥10 at 2 consecutive visits	All patients; < 90; ≥90
Systolic BP or Diastolic BP (mm Hg) (sitting)	Sustained Elevation	Meeting criteria for systolic BP for 2 consecutive visits or meeting criteria for diastolic BP for 2 consecutive visits or both	All Patients
Pulse (bpm) (sitting)	Low	<50 and decrease ≥15	All patients; ≥50; <50
	High	>100 and increase ≥15	All patients; ≤100; >100
	Sustained Elevation	>100 and increase ≥15 at 2 consecutive visits	All patients; ≤100; >100
Weight (kg)	Low	(Loss) decrease ≥7%	All patients
	High	(Gain) increase ≥7%	All patients
Temperature (° F)	Low	<96° F and decrease ≥2° F	≥96°F
	High	≥101° F and increase ≥2° F	<101°F

Abbreviations: BP = blood pressure; bpm = beats per minute; F = degrees Fahrenheit; kg = kilograms; mm Hg = millimeters of mercury; PCS= Potentially Clinically Significant.

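### A blood pressure or pulse elevation that first appears at Visit 12 and then stays at a similar level is counted as sustained in neither study phase

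*SAP*

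**What the plan says.** SAP 5.5.12.1.3, Table 5.7, defines sustained elevation as "≥140 and increase ≥20 at 2 consecutive visits" for systolic pressure, "≥90 and increase ≥10 at 2 consecutive visits" for diastolic pressure and ">100 and increase ≥15 at 2 consecutive visits" for pulse. A fourth row takes either pressure.

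The phases are kept apart. SAP 5.5.12.1 says "Categorical safety analyses will only be conducted for Study Period III and Study Period IV separately", and SAP 5.5.12 says "For Study Period III and IV combined, only the change from baseline with MMRM analysis (Section 5.5.10.1) will be conducted". Protocol 9.5 similarly limits the combined phases to repeated-measures and time-to-event analyses.

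The windows and baselines are in SAP 5.5.1.5, Table 5.5. The Study Period III row, "Treatment emergent changes in blood pressure, pulse, and ECGs", takes the last non-missing value of Visits 1-3 as baseline and Visits 3.01-12 as post-baseline. The matching Study Period IV row takes the last non-missing value of Visits 1-12 as baseline and Visits 12.01-14 as post-baseline. SAP 5.5.12.1.3 repeats this in words ("for other study phases, the baseline is defined as the last non-missing value before patients enter the study phases of interest") and applies it to every blood pressure and pulse analysis, categorical ones included. Study Period III categories are compared by Fisher's exact test; Study Period IV categories are only described.

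**The concern.** The sustained rows exist to separate a lasting elevation from a single high reading. An elevation that starts at the last visit of Study Period III has no second visit inside that window, and the reading that should begin the run is then used as the baseline for the next phase. A patient can have three elevated readings in a row (Visits 12, 13 and 14) and appear in neither sustained row.

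At stake is the completeness of the only by-arm counts of persistent blood pressure and pulse elevation in the SAP. Protocol 2.1 lists hypertension among the most frequent adverse events in two earlier migraine studies, although the same paragraph reports no other clinically important changes on cardiovascular monitoring. Protocol 4.3 gives safety during wash-out as the purpose of the follow-up phase, and this is where the baseline is reset.

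**Working it through.** The plan states no figure for this point, so there is none to reproduce. The check applies the written rules to visit sequences.

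**Inputs.** Protocol Appendix 2 schedules vital signs after the first dose at Visits 5, 6, 7, 8, 10 and 12 (Study Period III), at Visits 13 and 14 (Study Period IV), and at early termination. Thresholds come from Table 5.7; windows and baselines from Table 5.5.

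**Rule.** Let B be the last non-missing value of Visits 1-3 and y(k) the reading at Visit k. For systolic pressure:
- Study Period III requires y(k) ≥ 140 and y(k) − B ≥ 20 at two consecutive visits up to Visit 12. With onset at Visit 12 there is only one such visit, so the criterion cannot be met.
- Study Period IV uses y(12) as baseline. On scheduled visits it requires y(13) − y(12) ≥ 20 and y(14) − y(12) ≥ 20. A plateau gives differences near zero.

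Diastolic pressure (90, rise of 10) and pulse (above 100, rise of 15) work the same way.

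**Illustrative sequences** (readings assumed; visits before Visit 12 do not qualify):

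| Measure | B | V12 | V13 | V14 | V12 − B | V13, V14 minus V12 | Sustained in III | Sustained in IV | Sustained across III/IV against B |
|---|---|---|---|---|---|---|---|---|---|
| Systolic | 124 | 148 | 150 | 149 | +24 | +2, +1 | no | no | yes |
| Systolic | 120 | 145 | 145 | 145 | +25 | 0, 0 | no | no | yes |
| Diastolic | 75 | 92 | 92 | 92 | +17 | 0, 0 | no | no | yes |
| Pulse | 75 | 105 | 105 | 105 | +30 | 0, 0 | no | no | yes |
| Systolic | 120 | 142 | 164 | 165 | +22 | +22, +23 | no | yes | yes |
| Diastolic | 75 | 91 | 102 | 103 | +16 | +11, +12 | no | yes | yes |
| Pulse | 75 | 102 | 118 | 119 | +27 | +16, +17 | no | yes | yes |

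The first four rows are the gap. The last three show the one way to qualify in Study Period IV: a second full rise on top of the first.

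**Two boundary cases.** An unscheduled recheck after Visit 12 is Visit 12.01 and so belongs to Study Period IV; a reading of 146 after 145 at Visit 12 adds +1 and changes nothing. An elevation already present at Visit 10 and still present at Visit 12 (120, then 145 and 145) is sustained in Study Period III and is not affected.

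**Size.** If a share p of persistent elevations in completers begins at Visit 12 and then plateaus, the share missed is p. The documents give no onset distribution, so p could in principle lie anywhere from 0 to 1. Equal chance at the six visits gives p = 1/6 = 16.7%.

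**Timing of confirmation.** Visit 13 is targeted 60 days after Visit 12. The last dose is at Visit 10, so Visit 13 falls 15 + 15 + 60 = 90 days, about 3 months, after it.

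**Early termination.** Protocol 7 moves patients who stop during Study Period III directly into Study Period IV, so the early-termination reading probably plays the part of Visit 12. Table 5.5 gives that visit no number, so this is an inference.

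**The case against.** The opposing case is substantial.

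- **The baseline is deliberate.** SAP 5.5.12.1.3 explains that the last value before a phase limits confounding from medication being stopped or stabilised during screening, and uses the same approach in later phases for consistency. That stands as a reason for the phase-specific analyses. It does not address an on-treatment elevation carried into follow-up.
- **Every two-visit rule has an edge.** An onset at the last visit of any window cannot be confirmed inside it, and the rule treats all arms alike. If each arm lost the same 1/6, the ratio of incidences would be unchanged. This stands.
- **Confirmation across the boundary is imperfect.** Visit 13 comes well after the last dose. The stable-dose condition in Protocol Table CGAH.3 for ACE inhibitors, angiotensin receptor blockers and similar drugs runs only to Visit 12, and preventive medication may be started from one month later. This is a good reason not to redefine the Study Period III comparison.
- **The patient is visible elsewhere.** The Study Period III High row counts the patient, the abnormal-findings listing in SAP 5.8.2 covers both phases, the combined MMRM uses the readings, and Protocol 8.4.2 makes a clinically significant finding that results in a diagnosis an adverse event. None of these gives the incidence of persistent elevation by arm: the High row cannot tell one reading from several, a listing gives no rate, the MMRM estimates a mean, and adverse events depend on a diagnosis being made.

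A reader might infer that such an elevation can never count, or that the rule hides a treatment effect. The documents support neither. The second-rise sequences above do count in Study Period IV, and nothing in the plan shows that onset timing, or stopping because of blood pressure, differs by arm. Protocol 7.1.1 lists no blood pressure or pulse criterion for stopping treatment.

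**Conclusion.** The gap is real and narrow. A blood pressure or pulse elevation first seen at Visit 12 that persists at a similar level is sustained in neither phase, and no combined categorical analysis recovers it. For Visit 12 this follows from the text alone. For early termination it is probable but rests on the inferred visit mapping.

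The number of patients affected is unknown. One in six should not be read as an expected rate, since it assumes uniform onset over six visits. Nor should it be inferred that every patient who stops treatment when an elevation appears is missed: the protocol does not say that the early-termination visit is the one where the elevation is first seen, and a separate visit could supply a second Study Period III reading. What is established is a possible undercount in a supplementary safety table, with no between-arm bias shown and no bearing on the efficacy analyses. It is worth closing because doing so is cheap.

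**What to change.** Keep the Study Period III and Study Period IV analyses unchanged. Add one supplementary, descriptive Study Period III/IV row for each sustained criterion in Table 5.7 (systolic, diastolic, either pressure, pulse), with consecutive visits running from 3.01 to 14 and the last non-missing value of Visits 1-3 as baseline. SAP 5.5.12.1.3 already prescribes a pre-randomisation baseline for analyses that include the double-blind phase, so no new definition is needed. Run the rows at final database lock with the other Study Period III/IV outputs in SAP 5.8.3.

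Three sentences need a matching exception: those in SAP 5.5.12 and 5.5.12.1, and the combined-phase limit in Protocol 9.5. There is a precedent, since SAP 5.5.12.1.6 already summarises treatment-emergent anti-drug antibodies over the two phases combined. Table 5.5 needs one added line, which should also say how the early-termination visit is mapped. Protocol 9.2 allows SAP changes only before unblinding, so the text should be in place by then.

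The cost is a few lines of SAP text and one table run on data already collected. The downside belongs in a footnote: the confirming reading may come about 60 days after Visit 12 and about 3 months after the last dose, when concomitant or preventive medication may have changed. The row will also count pairs that lie wholly in Study Period IV, so it helps to state how many patients qualify only through a pair that spans the boundary.
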